#### 5.3.3.2 Secondary Efficacy Endpoints

**5.3.3.2.1 Lesion success**, defined as attainment of <30% residual stenosis, as measured by quantitative coronary angiography (QCA) using any percutaneous method [evaluated post-procedure]

**5.3.3.2.2 Device success**, defined as attainment of <30% residual stenosis of the target lesion measured by QCA using the assigned device [evaluated post-procedure]

**5.3.3.2.3 Procedure success**, defined as lesion success without the occurrence of in-hospital MACE [evaluated in-hospital]

**5.3.3.2.4 Clinically-driven target lesion revascularization (TLR)** [evaluated in-hospital and at 30 days, 6 months, and 1, 2, 3, 4, and 5 years]

**5.3.3.2.5 Clinically-driven target vessel revascularization (TVR)** [evaluated in-hospital and at 30 days, 6 months, and 1, 2, 3, 4, and 5 years]

**5.3.3.2.6 Target vessel failure (TVF)**, defined as cardiac death, target vessel-related MI, or clinically-driven target vessel revascularization [evaluated in-hospital and at 30 days, 6 months, and 1, 2, 3, 4, and 5 years]

**5.3.3.2.7 Target Lesion Failure (TLF)**, defined as cardiac death, target vessel-related MI, or clinically-driven target lesion revascularization [evaluated in-hospital and at 30 days, 6 months, and 2, 3, 4, and 5 years]

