Lesion success	Attainment of <30% residual stenosis (post-procedure), as measured by QCA using any percutaneous method
Long-term safety and efficacy	Target lesion failure between 12 months and 5 years by landmark analysis
Major adverse cardiac events (MACE)	All-cause death, myocardial infarction, or target vessel revascularization (reported as a composite)
Mortality	See "death"
Myocardial infarction (MI)	The primary protocol definition of myocardial infarction is the modified Third Universal Definition  provided in the Table below, which will be adjudicated and classified by an independent CEC.  In addition, the CEC will also adjudicate PCI-related MI according to several alternate thresholds of cTn (3, 10, 35, and 70 × 99th percentile URL), and all MI types (except Type 3) will be tabulated according to multiples of the 99 th percentile URL of cTn as recommended by Thygesen et al. 

Definition of Myocardial Infarction
--------------------------------------------

Criteria for acute myocardial infarction
-------------------------------------------------

The term acute MI should be used when there is evidence of myocardial necrosis in a clinical setting consistent with acute myocardial ischemia. Under these conditions any one of the following criteria meets the diagnosis for MI:

- Detection of a rise and/or fall of cardiac biomarker values (preferably cTn)\* with at least one value above the 99th percentile URL and with at least one of the following:
  - Symptoms of ischemia
  - New or presumed new significant ST–T changes or new LBBB
  - Development of pathological Q waves in the ECG
  - Imaging evidence of new loss of viable myocardium or new regional wall motion abnormality
  - Identification of an intracoronary thrombus by angiography or autopsy
- Cardiac death with symptoms suggestive of myocardial ischemia and presumed new ischemic ECG changes or new LBBB, but death occurred before cardiac biomarkers were obtained, or before cardiac biomarker values would be increased.

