### 2.2.2 Secondary Efficacy Endpoints

#### 2.2.2.1 Lesion Success

Lesion success is defined as attainment of <30% in-stent residual stenosis, as measured by quantitative coronary angiography (QCA) using any percutaneous method [evaluated post-procedure].

In-stent residual stenosis, as assessed by the Angiographic Core Laboratory, will be calculated using the following formula based on post-procedure (final) stent measurements:

$$\text{In-stent Residual Stenosis} = 100 * (1 - \text{mean (MIN1, MIN2)}) / \text{mean (IS1, IS2)}$$

Where

MIN1, MIN2: In-stent minimum lumen diameter from projections 1 and 2, respectively.

IS1, IS2: Interpolated in-stent reference vessel diameter from projections 1 and 2, respectively.

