**Table 2: Derivation of QCA Data**

	Pre-Procedure Pre-procedure QCA section of the ACL Case Report Form	In-Segment Final QCA section of the ACL Case Report Form	In-Stent Final Stent Measurements section of the ACL Case Report Form
Minimum Lumen Diameter (MLD) [mm]	Pre-procedure MLD = Mean of pre-procedure QCA MLDs from Projections 1 and 2	In-segment MLD = Mean of Final QCA MLDs from Projections 1 and 2	In-stent MLD = Mean of Min Stent from Projection 1 and Min Stent from Projection 2
Reference Vessel Diameter (RVD) [mm]	Pre-procedure RVD (mm) = Mean of pre-procedure QCA interpolated RVDs (Inter Normal) from Projections 1 and 2	In-segment RVD (mm) = Mean of Final QCA Interpolated RVDs (Inter Normal) from Projections 1 and 2	In-stent RVD (mm) = Mean of Interpolated RVDs (Inter Stent) from Projections 1 and 2
Diameter Stenosis (DS) [mm]	$\%DS = 100 * (1 - \text{Pre-procedure MLD} / \text{Pre-procedure RVD})$	$\%DS = 100 * (1 - \text{In-segment MLD} / \text{In-segment RVD})$	$\%DS = 100 * (1 - \text{In-stent MLD} / \text{In-stent RVD})$
Acute Gain (mm)	N/A	Post-procedure In-segment MLD – Pre-procedure MLD	Post-procedure In-stent MLD – Pre-procedure MLD

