#### 4.3 General Methods

All data collected will be summarized overall and by treatment. Descriptive statistics of continuous variables will include mean, standard deviation, median, quartiles, range, and sample size. Differences between the treatment arms, where specified, will be summarized with the differences of the two means, 95% confidence intervals for the difference between the means, and p-values based on a t-test. The distributions within each group will be tested for normality using the Shapiro-Wilks test and if normality cannot be assumed then a Wilcoxon rank-sum test for medians will be performed. The confidence interval for the difference of two means will be calculated under the assumption of unequal variances.

For categorical variables, descriptive statistics will include count, percentage, and sample size. Categorical data will be presented as n/N (%), and percentages will be rounded and reported to a single decimal point (xx.x %). Unless otherwise noted, subjects with missing data will be excluded from the denominator. Differences between the two treatment arms, where specified, will be summarized with the difference in percentages, the asymptotic 95% confidence interval for the difference of two percentages, and a p-value based on a chi-squared test. If 20% or more of the expected cell frequencies are less than 5 then a Fisher's Exact Test will be used to test for differences in proportions.

Survival analysis techniques will be used to analyze the time-to-event variables that occur at or after 30 days of follow-up. Time to event analysis will be performed for each time point separately (i.e. up to 30 days, 6-months (180 days), 1 year (365 days), 2 years (730 days), 3 years (1095 days), 4 years (1460 days), and 5 years (1825 days)) and summarized using the Kaplan-Meier estimated event rates and number of events. The log-rank test will be used for comparing treatments. Hazard ratios and the associated two sided confidence intervals (Wald's CI) will be estimated by Cox proportional hazards model, including treatment as a covariate.

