#### **4.4 Methods to Manage Missing Data**

Reasonable efforts will be made to obtain complete data for all patients; however, missing observations may occur. The reasons for missing data will be reported (e.g., patient is deceased, lost to follow up, withdrew consent, missed follow-up visit, etc.).

The primary endpoint analysis of TLF will be performed using all available data. As a sensitivity analysis, a tipping point analysis will be performed to assess the impact of missing values from subjects with insufficient 12 month follow-up. This analysis will include the worst-case scenario as the most extreme case.

All secondary endpoint analyses will be performed using all available data.

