### 5.3.2 Secondary Efficacy Endpoints

Lesion Success will be assessed on a lesion level, performed on the ITT analysis population, and presented for overall subjects and by treatment arm. The analysis of Device Success will include all

	FORM	Document No BIO-TMP-0702 Revision: 00
	TITLE Statistical Analysis Plan	Effective date: 16-Mar-2018 Department: BIO

target lesions in which the assigned device is attempted in the denominator [1]. As a secondary analysis, the device success analysis will include all target lesions in the denominator, whether or not an attempt to implant the assigned device was made.

No formal hypothesis testing will be performed. Both endpoints will be compared descriptively between the treatment arms using a generalized linear mixed model that accounts for the clustering effect of multiple lesions per subject. The model includes treatment as a fixed effect and subject as a random effect. Two sided 95% CI for the estimated difference and p-values will be reported.

Procedural success and in- hospital TVR, TLR, TVF, and TLF events will be evaluated in the ITT analysis population. No formal hypothesis testing will be performed. Descriptive statistics will include count, percentage, and sample size. Subjects with missing data will be excluded from the denominator. Differences between the two treatment arms will be summarized descriptively with the difference in percentages, the asymptotic 95% confidence interval for the difference of two percentages, and a p-value based on a chi-squared test. If 20% or more of the expected cell frequencies are less than 5 then a Fisher's Exact Test will be used to test for differences in proportions.

Survival analysis techniques, as detailed in Section 4.3, will be used to analyze the TVR, TLR, TVF, and TLF events at 30 days, 6 months, and 1, 2, 3, 4, and 5 years. Summary statistics will include Kaplan-Meier estimated event rates and number of events. The log-rank test will be used for comparing treatments. Hazard ratios and the associated two-sided confidence intervals (Wald's CI) will be estimated by Cox proportional hazards model, including treatment as a covariate.

A secondary analysis of all secondary efficacy endpoints will also be performed in the PP analysis population.

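### The SAP limits lesion success to in-stent stenosis, so target lesions that end without a stent have no defined score in lesion or procedure success

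*SAP*

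**What the plan says.** Protocol 5.3.3.2.1 has lesion success "defined as attainment of <30% residual stenosis, as measured by quantitative coronary angiography (QCA) using any percutaneous method". Appendix A (17.1, entry for lesion success) repeats it: "Attainment of <30% residual stenosis (post-procedure), as measured by QCA using any percutaneous method". Neither text mentions a stent.

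SAP 2.2.2.1 reads: "Lesion success is defined as attainment of <30% in-stent residual stenosis, as measured by quantitative coronary angiography (QCA) using any percutaneous method". The stenosis "will be calculated using the following formula based on post-procedure (final) stent measurements", with in-stent minimum lumen diameter and in-stent reference diameter as inputs. SAP Table 2 also derives an in-segment value from the final QCA ("In-segment MLD = Mean of Final QCA MLDs from Projections 1 and 2"), but lesion success does not use it.

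On missing values, SAP 4.3 says of categorical variables: "Unless otherwise noted, subjects with missing data will be excluded from the denominator". SAP 4.4 says: "All secondary endpoint analyses will be performed using all available data". In SAP 5.3.2, the paragraph on procedural success and in-hospital events says: "Subjects with missing data will be excluded from the denominator". The text on lesion success in 5.3.2 specifies a lesion-level mixed model in the ITT population. It gives neither a denominator nor a rule for a lesion without a stent.

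Device success (SAP 2.2.2.2) is treated differently. It has a primary denominator of attempted lesions and a secondary denominator of all target lesions. It also has a list of failure reasons that includes PCI not attempted and no device implanted.

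**The concern.** The SAP keeps the Protocol's allowance for any percutaneous method but adds a measurement that exists only where a stent was placed. Both cannot hold for a lesion treated by balloon alone, or for one that was never crossed. The SAP says it is based on Protocol version 8.0, and it gives no reason for the narrowing.

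Two programmers could follow this SAP and report different rates: one dropping unstented lesions, the other scoring them as not attaining the threshold. Neither would reproduce the Protocol endpoint, because a balloon-only lesion with less than 30% residual stenosis is a Protocol success under neither approach. Procedure success is built on lesion success (SAP 2.2.2.3) and inherits the gap. If the share of unstented lesions differed between the devices, the descriptive comparison would depend on an unstated choice.

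**Working it through.** The documents give no expected rate, power or count for lesion or procedure success, so there is no figure to reproduce. The check compares the texts and then illustrates the effect under stated assumptions.

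**Step 1: a target lesion that ends with no stent**

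- Balloon only, residual stenosis below 30%: success under the Protocol; no value under SAP 2.2.2.1.
- Balloon only, residual stenosis 30% or more: failure under the Protocol; no value under the SAP.
- Untreated or uncrossed: failure under the Protocol, since eligibility requires a visually estimated stenosis of at least 50% (Protocol 6.2.1.2.3); no value under the SAP.
- Assigned device fails but another stent is implanted: an in-stent value exists, so the lesion is scored under both.

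Only lesions with no stent at all are affected.

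**Step 2: which rule would remove them**

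The exclusion sentences in SAP 4.3 and 5.3.2 speak of subjects, and the one in 5.3.2 stands in the procedural-success paragraph. For the lesion-level analysis, removal follows only from the available-data sentence in SAP 4.4 together with a mixed model that omits records without an outcome. That is a likely default, not a stated rule.

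**Step 3: procedure success**

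- In-hospital MACE: the subject fails whatever the lesion value.
- No MACE, one successful stented lesion and one unstented lesion: the Protocol's Appendix A entry requires every lesion to succeed, so the unstented lesion decides. SAP 4.3 says one lesion suffices for patient-level endpoints, so the same subject could be a success.
- No MACE, no stented target lesion: no lesion value exists, and SAP 5.3.2 could remove the subject from the denominator.

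**Step 4: direction**

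Let *s* be success among stented lesions, *u* the share of target lesions left unstented, and *b* the share of those that are balloon-only with less than 30% stenosis.

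- Protocol rate: s(1 − u) + bu
- Unstented lesions dropped: s. Error: s − [s(1 − u) + bu] = u(s − b)
- Unstented lesions read as non-attainment: s(1 − u). Error: −bu

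With assumed s = 98% and u = 2%:

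| b (assumed) | Protocol rate | Error if dropped | Error if non-attainment |
|---|---|---|---|
| 0 | 96.04% | +1.96 points | 0 |
| 0.5 | 97.04% | +0.96 points | −1.00 point |
| 1 | 98.04% | −0.04 points | −2.00 points |

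Dropping raises the rate when b < s and lowers it when b > s. Reading the lesions as non-attainment can only lower it.

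**Step 5: size if all unstented lesions are failures (b = 0)**

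The overstatement from dropping is s × u. With s = 98%:

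- u = 0.5%: 98.0% against 97.5%, 0.49 points
- u = 1%: 98.0% against 97.0%, 0.98 points
- u = 2%: 98.0% against 96.0%, 1.96 points
- u = 3%: 98.0% against 95.1%, 2.94 points

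**Step 6: if the share differs by arm**

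Take the planned 1088 and 544 subjects, one lesion each, s = 98% in both arms, b = 0, and a normal-approximation interval. Dropping gives a difference of 0 in both cases below. Scoring the lesions as failures gives:

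- u = 3% against 1%: 0.98 × 0.97 − 0.98 × 0.99 = −1.96 points (95% CI −3.88 to −0.04)
- u = 2% against 1%: 0.98 × 0.98 − 0.98 × 0.99 = −0.98 points (95% CI −2.82 to 0.86)

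**The case against.** The SAP never calls an unstented lesion missing. Its endpoint is attainment of a threshold, and a lesion without a stent can be read as not attaining it. The SAP takes that view for device success, with parallel wording. This stands: a reader might infer that the SAP removes unstented lesions by rule, and it does not. The defect is an undefined score.

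A reader might also infer that success is necessarily biased upward and that delivery failures are hidden. The documents support neither. The sign depends on which reading is applied and on how many unstented lesions are balloon-only successes. A failed delivery followed by another stent stays in lesion success. Lesions with an attempted implant are in the primary device-success denominator, all target lesions are in the secondary one, and failure reasons are tabulated. A deliverability difference would show there.

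Every rate in the illustration is assumed. Eligibility requires lesions to be treatable with a single study stent, and nothing in the documents suggests that several percent end unstented.

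The objection does not remove the departure from the Protocol. Whether dropped or read as non-attainment, a balloon-only lesion below 30% is not counted as the success the Protocol makes it.

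**Conclusion.** The point holds as a definition and denominator gap. SAP 2.2.2.1 departs from the Protocol, leaves lesion success uncomputable for target lesions without a stent, and gives no denominator rule. Exclusion is the likely default. Loss of a subject from procedure success is clear only for someone with no in-hospital MACE and no stented target lesion.

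Direction and size are unknown, because the documents contain no unstented rate. The 0.5 to 2.9 points rest wholly on assumed inputs: 98% success in stented lesions, 0.5% to 3% unstented, and all of those true failures.

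Lesion and procedure success are descriptive, with no formal testing. Target lesion failure at 12 months and the powered secondary endpoint do not use them, so the primary conclusion does not change. This is a minor correction.

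**What to change.** In SAP 2.2.2.1, 2.2.2.3 and 5.3.2:

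- Make the lesion-success denominator all target lesions in the ITT population.
- Score target lesions that were treated but not stented on the final in-segment percent diameter stenosis already derived in Table 2.
- Count untreated or uncrossed target lesions as lesion-success failures.
- Treat only unreadable or lost angiograms as missing.
- State that procedure success requires every target lesion to succeed, as in Protocol Appendix A, and name this as an exception to the one-lesion rule in SAP 4.3.

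The cost is SAP wording and a small programming change. A few lesions would be scored in-segment while the rest are scored in-stent, which should be footnoted. Reported rates may be slightly less favourable.

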#### 2.2.2.2 Device Success

Device success is defined as attainment of <30% in-stent residual stenosis of the target lesion measured by QCA using the assigned device [evaluated post-procedure]. Lesions treated with multiple stents in which one stent is an assigned device and  $\geq 1$  is not the assigned device are considered as device failures.

This analysis is a lesion-level analysis performed in the ITT subject population. The primary analysis will include all target lesions in which implantation of the assigned device is attempted in the denominator. As a secondary analysis, the device success analysis will include all target lesions in the denominator, whether or not an attempt to implant the assigned device was made.

In addition, lesions without device success will be reported according to the following classification adapted from the 2019 EAPCI/ESC position statement (Chang et al. Defining Device Success for Percutaneous Coronary Intervention Trials: A Position Statement from the European Association of Percutaneous Cardiovascular Interventions of the European Society of Cardiology. *Eurointervention* 2019; Jaa-642 2019, doi 10.4244/EIJ-D-19-00552) [1] in a lesion-level analysis:

	FORM	Document No BIO-TMP-0702 Revision: 00
	TITLE Statistical Analysis Plan	Effective date: 16-Mar-2018 Department: BIO

- 1) PCI was not attempted
- 2) No device implanted (with or without implant attempt)
- 3) Non-assigned device implanted without attempt to use the assigned device
- 4) Unsuccessful device delivery (i.e., implant attempted but no device ultimately implanted)
  - a) Without crossover to non-assigned devices (i.e., attempted implant of assigned device; did not attempt to implant unassigned device)
  - b) Crossover to non-assigned devices, but still unsuccessful (i.e., attempted to implant assigned device; attempted implant of unassigned device)
- 5) Device implanted outside the intended location
- 6) Non-assigned device implanted after a failed attempt to use the assigned device
- 7) Non-assigned device implanted after successful implantation of assigned device(s)
- 8) Residual stenosis above accepted thresholds (NOTE: threshold is  $\geq 30\%$  based on protocol definition of device success)

Reasons for absence of device success will be summarized based on the breakdown listed above and the analysis will be performed in the ITT subject population in 1) all target lesions in which implantation of the assigned device is attempted in the denominator (primary), and 2.) all target lesions (secondary).

#### **2.2.2.3 Procedure Success**

Procedure success is defined as lesion success without the occurrence of in-hospital major adverse cardiac events (MACE) [evaluated in-hospital]. MACE is a composite of all-cause death, myocardial infarction, and target vessel revascularization and will be adjudicated by an independent Clinical Events Committee (CEC). The myocardial infarction (MI) events will be adjudicated per the modified Third Universal Definition.

#### **2.2.2.4 Clinically Driven Target Lesion Revascularization**

Target lesion revascularization (TLR) is defined as any repeat percutaneous intervention of the target lesion or bypass surgery of the target vessel performed for restenosis or other complication of the target lesion. The target lesion is defined as the treated segment from 5 mm proximal to the stent and to 5 mm distal to the stent.

A revascularization is considered clinically driven if angiography at follow-up shows a percent diameter stenosis  $\geq 70\%$  (by core lab quantitative coronary angiography assessment) OR percent diameter stenosis  $\geq 50\%$  (by core lab quantitative coronary angiography assessment) accompanied by one of the following:

- (1) a positive history of recurrent angina pectoris, presumably related to the target vessel;

	FORM	Document No: BIO-TMP-0702 Revision: 00
	TITLE Statistical Analysis Plan	Effective date: 16-Mar-2018 Department: BIO

- (2) objective signs of ischemia at rest (ECG changes) or during exercise test (or equivalent) presumably related to the target vessel;
- (3) abnormal results of any invasive functional diagnostic test (e.g., Doppler flow velocity reserve, fractional flow reserve).

All TLRs will be adjudicated and categorized by the CEC as clinically indicated or not clinically indicated based on the above protocol definition and will be evaluated in-hospital and at 30 days, 6 months, and 1, 2, 3, 4, and 5 years.

#### **2.2.2.5 Clinically Driven Target Vessel Revascularization**

Target vessel revascularization (TVR) is defined as any repeat percutaneous intervention or surgical bypass of any segment of the target vessel. The target vessel is defined as the entire major coronary vessel proximal and distal to the target lesion, which includes upstream and downstream branches and the target lesion itself.

A revascularization is considered clinically driven if angiography at follow-up shows a percent diameter stenosis  $\geq 70\%$  (by core lab quantitative coronary angiography assessment) OR percent diameter stenosis  $\geq 50\%$  (by core lab quantitative coronary angiography assessment) accompanied by one of the following:

- (1) a positive history of recurrent angina pectoris, presumably related to the target vessel;
- (2) objective signs of ischemia at rest (ECG changes) or during exercise test (or equivalent) presumably related to the target vessel;
- (3) abnormal results of any invasive functional diagnostic test (e.g., Doppler flow velocity reserve, fractional flow reserve).

All TVRs will be adjudicated and categorized by the CEC as clinically indicated or not clinically indicated based on the above protocol definition and will be evaluated in-hospital and at 30 days, 6 months, and 1, 2, 3, 4, and 5 years.

